### **2. Study Population**

#### Inclusion Criteria

Birth weight  $\leq 1250$  grams, indwelling arterial catheter, age  $< 24$  hrs old

#### Exclusion Criteria

Lethal chromosomal abnormality, major congenital anomaly, decision not to provide full intensive care support, or skin integrity insufficient to allow placement of NIRS sensors

#### Enrollment of Subjects

Each participating center will be responsible for obtaining their own IRB approval and devising a screening strategy to identify potential subjects. Informed parental consent will be obtained prior to enrollment, either prenatally or postnatally.

### **3. Study Intervention/ Data Collection**

After enrollment, a NIRS neonatal sensor (Covidien) will be placed on the infant's forehead for continuous monitoring of cerebral saturation. Clinicians will be blinded to  $rSO_2$  measures by obscuring the monitor with a shield. NIRS sensors will be assessed on a daily basis to evaluate surrounding skin integrity and replaced as necessary. NIRS data in addition to continuous patient data including blood pressure and systemic oxygen

saturation will be acquired at a sampling rate of 1/30 Hz until 96 hours of life. Data will be collected using a Vital Sync bedside device allowing for data integration from the bedside monitor and INVOS. Blood pressure readings will be obtained from an indwelling arterial catheter. All data will be downloaded to media for secure electronic submission and subsequent processing by a central analyst. Data will be identified by study number only and will be maintained in a secure location. Total time with missing data will be ascertained. Of the remaining useful NIRS data, mean rSO2 and PPI (total percentage time with concordance between rSO2 and mean arterial blood pressure as determined in the very low frequency range (1/30 Hz)) will be calculated over 20 minute intervals. Concordance will be defined as a Pearson's correlation coefficient >0.5. Percentage of time with cerebral rSO2 <40% will be defined as a low rSO2 index. Blood gas pCO2 levels will be collected for possible confounding effects of hypocarbia or hypercarbia on cerebral blood flow. Perinatal data including birth weight, gestational age, sex, time of blood transfusions, use of pressors, and Score for Neonatal Acute Physiology Perinatal Extension II (SNAPPE-II) will be utilized.

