**February 18, 2016**

## **A. Problem Statement/ Rationale**

Extremely preterm infants are at high risk for early hemodynamic instability. Poor modulation of vascular tone, variable responses to agitation, sepsis, development of a hemodynamically significant patent ductus arteriosus (hsPDA), and other factors may contribute to fluctuations in systemic blood pressure in the first few days of life. Moreover, preterm infants are at risk for altered cerebral autoregulation with increased periods of cerebral pressure passivity, potentially leading to the development of intraventricular hemorrhage (IVH) or white matter injury. It remains unclear whether disturbances in systemic blood pressure also result in compromised end organ perfusion. Near-infrared spectroscopy (NIRS) is a non-invasive technology, well suited to bedside monitoring of regional tissue oxygenation in these infants. *This protocol will investigate the utility of early NIRS measures in identifying preterm infants at highest risk for mortality and significant neonatal CNS morbidities including IVH and periventricular leukomalacia (PVL).* The novel approach of measuring regional tissue oxygenation as an indicator of end-organ perfusion may contribute substantially to the literature as well as to clinical practice. NIRS monitoring will provide the clinician with evidence of abnormal cerebral tissue oxygenation and impaired cerebral autoregulation. *We hypothesize that abnormal NIRS measures and increased cerebral pressure passivity in extremely preterm infants in the first 96 hours of life will be associated with mortality and the development of severe CNS morbidities.*

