### **Impairment of cerebral autoregulation**

Preterm infants are at higher risk for impaired cerebral autoregulation, which can also be readily detected using NIRS. NIRS measures of  $\text{rSO}_2$  provide a good estimate of cerebral blood flow. [8-10] This approximation has been validated in animal studies using the gold standard radioactive microsphere technique [11, 12] and confirmed by transcranial Doppler ultrasound as a reliable method to assess for impaired cerebral autoregulation. [10] Specifically, concordance between mean arterial blood pressure and  $\text{rSO}_2$  indicates a pressure passive cerebral circulation and presumed loss of autoregulation. [11, 13] The prevalence of pressure passivity has been quantified using a PPI defined as the percentage of 10-min epochs with significant coherence between mean arterial pressure (MAP) and  $\text{rSO}_2$  signals in the low frequency range. [11] A NIRS study in preterm infants found that cerebral pressure passivity signifying loss of autoregulation occurred in a majority of premature infants with a mean PPI of 20%. [11]

Pressure passivity was associated with low gestational age and birth weight, systemic hypotension, and maternal hemodynamic factors. Loss of autoregulation with concordant changes between MAP and cerebral oxygenation in preterm infants was also significantly associated with increased severe IVH and PVL [12, 14] and with mortality [15] in single center studies.

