##### Statistical Analysis

Analyses will include mixed effects regression models for repeated measures to examine the relationship between NIRS measures of low rSO2 index, PPI, and the outcome of CNS-morbidity or in-hospital mortality. Analyses will be adjusted for gestational age, birth weight, sex, center, and SNAPPE-II. Secondary analyses may look at additional NIRS measures as predictors including fractional tissue oxygen extraction (FTOE) and degree of variability in cerebral saturation levels.

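### PPI takes no account of how far MAP moved in each interval, so at a given degree of passivity it rises with blood pressure variability, which the planned model does not separate

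*Combined protocol and SAP*

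**What the plan says.** Methods section 3 (Study Intervention/ Data Collection) has arterial pressure, rSO2 and systemic saturation "acquired at a sampling rate of 1/30 Hz until 96 hours of life". Mean rSO2 and PPI "will be calculated over 20 minute intervals". The index is "PPI (total percentage time with concordance between rSO 2 and mean arterial blood pressure", and the whole test for an interval is this: "Concordance will be defined as a Pearson's correlation coefficient >0.5".

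The section sets no minimum MAP change, uses no slope, and has no category for an interval that cannot be assessed. The one data-quality step is "Total time with missing data will be ascertained", after which PPI is computed on what remains.

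The Background section on impaired autoregulation gives the interpretation: concordance "indicates a pressure passive cerebral circulation and presumed loss of autoregulation".

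Under Statistical Analysis, "Analyses will be adjusted for gestational age, birth weight, sex, center, and SNAPPE-II". Neither the level nor the variability of blood pressure is listed. The optional secondary predictors include variability of cerebral saturation, but not of MAP.

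The Rationale (section A) expects unstable pressure in this population, from causes that "may contribute to fluctuations in systemic blood pressure in the first few days of life".

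**The concern.** Autoregulation shows itself only when pressure changes. If MAP is nearly constant for 20 minutes, the rSO2 trace is mostly noise from other sources. The correlation is then low whether the circulation is passive or not. Under the plan's rule such an interval usually lands on the not-concordant side and lowers PPI, as if autoregulation had been tested and found intact.

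Two infants with the same passivity can therefore have quite different PPI values because one has calmer pressure. The ordering can even reverse, with the more passive infant scoring lower.

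Aim 2 relates the degree of pressure passivity to death and severe CNS morbidity. If MAP variability is itself related to those outcomes, some of the PPI association will carry that relation, and nothing planned would show how much. The problem does not depend on serial correlation, since it is present with fully independent samples.

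**Working it through.** **The plan's own figure.** The documents compute nothing for this point. Their one calculated figure, 80% power with 100 infants and 8% of variance explained, is not affected. It reproduces by Fisher's z: r = √0.08 = 0.283, atanh(r) = 0.291, 0.291 × √97 − 1.96 = 0.90, which gives power of about 82%.

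**Inputs from the plan.** One sample per 30 seconds over 20 minutes gives 40 samples per interval. Three intervals per hour for 96 hours gives at most 288 intervals. Concordance is r > 0.5.

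**Inputs assumed.** Gain, rSO2 noise SD, MAP SD and autocorrelation are not in the documents and are assumed throughout.

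**Step 1: expected correlation.** Let rSO2 = gain × MAP + noise, with passivity present in every interval. Then

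ρ = gain × SD(MAP) / √[gain² × SD(MAP)² + SD(noise)²].

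This exceeds 0.5 only if gain × SD(MAP) > SD(noise)/√3 = 0.577 × SD(noise). With gain 0.3 points per mmHg and noise SD 1.5 points, MAP SD must exceed 0.577 × 1.5 / 0.3 = 2.9 mmHg.

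**Step 2: share of intervals scored concordant, independent samples.** The Fisher approximation is Φ{[atanh(ρ) − atanh(0.5)] × √37}, with atanh(0.5) = 0.549.

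| MAP SD (mmHg) | ρ | Fisher approximation | Simulated |
|---|---|---|---|
| 1 | 0.3/√(0.09+2.25) = 0.196 | 2% | 2% |
| 2 | 0.6/√(0.36+2.25) = 0.371 | 17% | 17% |
| 3 | 0.9/√(0.81+2.25) = 0.514 | 55% | 57% |
| 4 | 1.2/√(1.44+2.25) = 0.625 | 87% | 88% |

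With gain 0.5 the simulated shares are 9%, 70%, 98% and 100%.

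**Step 3: autocorrelated samples.** For gain 0.3, noise SD 1.5 and the same four MAP SDs:

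- lag-1 autocorrelation 0.8: 14%, 33%, 55%, 75%
- lag-1 autocorrelation 0.95: 26%, 41%, 56%, 69%

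The gradient flattens but remains.

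**Step 4: the floor.** With no MAP-driven signal and independent samples, t = 0.5 × √(38/0.75) = 3.56 on 38 degrees of freedom, so P(r > 0.5) is about 0.05%. By simulation the rate is 0.5%, 4%, 9% and 14% at autocorrelation 0.5, 0.8, 0.9 and 0.95. A fully passive infant whose pressure is very stable approaches this floor when rSO2 noise dominates.

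**Step 5: the other limits.** At gain 0 the share stays at the floor for every MAP SD, so MAP variability creates no concordance where there is no passivity. With little rSO2 noise PPI stays high: in the cell with gain 0.3, MAP SD 1 mmHg and independent samples, cutting noise SD from 1.5 to 0.5 raises it from 2% to 57%. With no noise it is 100% at any non-zero MAP SD.

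**Step 6: rank reversal.** With noise SD 3 and autocorrelation 0.5, gain 1 with MAP SD 1 mmHg gives 15%, while gain 0.3 with MAP SD 6 mmHg gives 56%.

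**Step 7: does a covariate help?** In simulated studies of 100 infants whose passivity differed, the outcome was driven only by MAP variability (assumed log-odds 0.7 per SD). PPI was significant in 34% to 77% of studies without a MAP-variability term and in about 4% with one.

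**The case against.** Three stronger readings are tempting, and the documents support none of them.

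- **That a fully passive infant with stable pressure scores near 0%.** That is a limiting case. It needs noise to dominate and weak autocorrelation (steps 3 to 5), and the documents give neither. The defensible statement is that such an infant can score as low as the chance rate, about 0% to 14%.
- **That a PPI association could come entirely from blood pressure variability.** That requires passivity not to differ between infants. The Background reports that it does differ, with gestational age, birth weight and hypotension, and the first two are adjusted for. Only part of an association can be put in question.
- **That the Rationale names pressure fluctuation as the route to injury.** It does not. It links potential injury to altered autoregulation with pressure passivity, and calls it unclear whether pressure disturbances compromise perfusion. The confounding path is plausible but not asserted by the plan.

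The remaining objections have some weight. This is an observational pilot on identifying high-risk infants, and an index that mixes passivity with pressure swings may still predict. The issue is then one of interpretation, but Aim 2 and the second hypothesis are worded in terms of passivity, so interpretation matters. If MAP is exactly constant, r is undefined and the plan gives no rule, so scoring as not concordant is certain only for near-flat intervals with low r. Gain and MAP SD act multiplicatively, so an additive covariate separates them imperfectly. MAP variability may also lie on the causal path, where adjustment would remove a real effect. These last two points argue for a sensitivity analysis and against changing the primary model.

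**Conclusion.** The point holds in a limited form. Because concordance rests on the correlation alone, PPI rises with within-interval MAP variability wherever some passivity exists, and no planned analysis shows how much of a PPI association is due to that. The direction follows from the formula for Pearson's r. The size does not follow from the documents: 2% to 88%, or 26% to 69%, over MAP SD 1 to 4 mmHg illustrates one assumed gain and noise level at two assumed autocorrelations. The covariate result in step 7 is equally an illustration. For a pilot this is a worthwhile refinement to the interpretation of Aim 2. It does not invalidate PPI or the primary analysis.

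**What to change.** Under Statistical Analysis, pre-specify one sensitivity model for PPI that adds the infant's mean log within-interval MAP SD to the listed covariates. Leave the primary model as it is and state the reason: MAP variability may be part of the causal path. Report the PPI coefficient from both models side by side.

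In section 3, define within-interval MAP SD from the arterial pressure already recorded, and say how an interval with constant MAP is handled. As a secondary check, report PPI restricted to intervals above a MAP SD cut-off, with the share of assessable intervals for each infant. Fix the cut-off from the pooled MAP data before outcomes are linked. State that a cut-off reduces the dependence without removing it: in step 2 PPI still climbs from 57% to 88% between MAP SD 3 and 4 mmHg.

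The cost is a few lines of code and one extra model, with no new data. The drawbacks are one more term in a model with 100 infants and five listed adjusters, and fewer intervals behind the restricted PPI.

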## **E. Methods:**

### **1. Study Design**

This multi-center, prospective observational pilot study will investigate NIRS monitoring of end organ oxygenation and cerebral autoregulation at six centers with previous NIRS experience with an estimated total enrollment of 100 infants over a one-year period. After enrollment, NIRS sensors will be applied to an infant's forehead to measure cerebral oxygenation within the first 96 hours of life. NIRS data, in addition to blood pressure and systemic oxygen saturation, will be continuously acquired until 96 hours of age or earlier if arterial access becomes unavailable. Data will be analyzed in 20-minute intervals to determine the mean cerebral oxygenation ( $rSO_2$ ) and pressure passivity index (PPI as defined below), as well as a low  $rSO_2$  index (time with  $rSO_2 < 40\%$ ). Statistical analyses will include logistic regression and longitudinal modeling to determine the association between these NIRS measures and the development of in-hospital mortality or severe neurologic morbidities as previously described.

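### PPI is tied to a frequency (1/30 Hz) that 30-second sampling cannot measure, and raw r > 0.5 has no chance reference

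*Combined protocol and SAP*

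**What the plan says.** Section E.3 (Study Intervention/ Data Collection) says that NIRS, blood pressure and systemic saturation data "will be acquired at a sampling rate of 1/30 Hz until 96 hours of life". PPI is the percentage of time with concordance between rSO2 and "mean arterial blood pressure as determined in the very low frequency range (1/30 Hz"). Mean rSO2 and PPI "will be calculated over 20 minute intervals", and the operating rule is "Concordance will be defined as a Pearson's correlation coefficient >0.5".

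No filter, detrending step, minimum number of valid samples per window or chance reference is stated there or in section E.4.

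PPI carries all of Aim 2 and Hypothesis 2 (sections B and C). It is one of the two NIRS predictors named for the main models in section E.4, which adjust for gestational age, birth weight, sex, center and SNAPPE-II.

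**The concern.** The same figure, 1/30 Hz, serves as the sampling rate and as the frequency at which concordance is assessed. A signal can be analysed only up to half its sampling rate, so the index is described by a property that the data cannot have, and the study report would repeat the error.

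Once that label is set aside, the plan defines no band. What remains is an unfiltered correlation on a short run of points, judged against a fixed cut-off of 0.5. How often unrelated signals pass that cut-off depends on how smooth they are. Smooth signals have few effectively independent points in 20 minutes and so reach r > 0.5 by chance more often than rough ones. At stake is whether an association between PPI and outcome can be read as impaired autoregulation.

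**Working it through.** **The plan's own figure.** The plan gives no chance level for PPI. Its only design calculation (section E.4) is 80% power with 100 infants at 0.05 if 8% of variance is explained. By Fisher z: r = √0.08 = 0.283; atanh(0.283) × √97 = 2.86; 2.86 − 1.96 = 0.90; power 81.7%. That figure reproduces and is not in question.

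**Inputs from section E.3.** Sampling rate 1/30 Hz; window 20 minutes (also in section E.1); threshold r > 0.5. I assume one correlation per window and no missing samples.

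**Frequency range.**
- Upper limit: (1/30)/2 = 1/60 Hz = 0.0167 Hz, a period of 60 s. The stated 1/30 Hz is twice this.
- A 1/30 Hz oscillation read every 30 s gives sin(2πk + φ) = sin φ at every sample k, which is a constant.
- Samples per window: 1200 s × 1/30 Hz = 40.
- Lowest frequency: 1/1200 Hz = 0.0008 Hz.

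**Chance of r > 0.5 for unrelated signals, 40 points.** With no autocorrelation, t = 0.5 × √(38/0.75) = 3.56 on 38 degrees of freedom, an upper tail of 0.05%. With autocorrelation, I simulated pairs of mutually independent first-order autoregressive series. The lag-1 autocorrelation at 30 s is an assumption, because the documents give none:

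| Lag-1 autocorrelation | Raw | After linear detrending |
|---|---|---|
| 0 | 0.05% | 0.06% |
| 0.5 | 0.4% | 0.4% |
| 0.8 | 4.4% | 3.7% |
| 0.9 | 9.6% | 7.1% |
| 0.95 | 13.9% | 9.1% |
| 0.98 | 17.3% | 10.1% |
| Random walk | 20% | 10.3% |

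Noise or unequal smoothness lowers these values. Random walks with a signal-to-noise variance ratio of 4 give 13.6%, and with a ratio of 1 give 2.8%. A 0.95 series paired with a 0.8 series gives 7.4%.

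**What reaches the association analysis.** A full 96-hour record has 96 × 3 = 288 windows. Over that many, simulated chance PPI varies between infants of equal smoothness with an SD of only 1.3 to 2.2 points, so random error largely averages out. A difference in smoothness does not. Infants with no pressure passivity would average 4.4% at autocorrelation 0.8 and 13.9% at 0.95, a gap of 9.5 points.

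**Does a time-shifted reference work?** In simulation, correlating rSO2 with the same infant's shifted MAP returned the chance level at autocorrelations of 0.8, 0.9 and 0.95 (about 4.4%, 9.6% and 14%), whether or not the unshifted signals were truly coupled.

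**The case against.** The strongest reply is that the parenthesis merely repeats the sampling rate. Pearson's r needs no band, correcting the figure changes no PPI value, and data below 1/60 Hz may still fairly be called very low frequency. This stands as an account of how the wording may have arisen. It leaves the text wrong and the usable band unstated.

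The second reply is that the aim is association, not prevalence. A chance level common to all infants acts much like a constant and drops out of a regression, and the random part is small. This stands too. Harm requires smoothness to differ with illness, which the documents neither show nor exclude. SNAPPE-II adjusts for illness severity but does not measure signal smoothness.

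Three stronger readings are tempting and are not supported:
- A reader might infer that PPI mainly reflects slow drift. That depends on autocorrelation: periods of 5 minutes or longer hold 20% of within-window variance for white noise, 74% at 0.8 and 87% for a random walk.
- A reader might set the 20% upper end beside the mean PPI of 20% cited in section D and conclude that the index is all chance. The cited figure came from 10-minute epochs with significant low-frequency coherence, a different measure, so the match is uninformative.
- A reader might infer that faster oscillations fold into the record. That would need single unaveraged readings, and the documents do not say how the 30-second values are formed.

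**Conclusion.** The stated frequency is one the design cannot measure; this follows from section E.3 alone and needs no assumption. It is also clear from the text that PPI has no chance reference.

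The size of the chance component is conditional: under 0.1% to about 20% of windows, and roughly 10% to 14% if lag-1 autocorrelation is 0.90 to 0.95. The top of the range needs two noise-free random walks. These figures rest on a first-order autoregressive model, equal smoothness in both signals and complete 40-point windows.

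The consequence for Aim 2 is a possible bias, not a demonstrated one. It arises only if smoothness tracks illness, and it would then produce an association with death or CNS injury that does not reflect autoregulation. The point does not show that PPI is invalid, and it leaves the power figure untouched. It warrants a correction of the text and an inexpensive safeguard.

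**What to change.** 1. In section E.3, replace the 1/30 Hz in the PPI definition with the band that the data support, about 0.0008 to 0.0167 Hz. Leave the sampling rate as it is.
2. Keep raw PPI (r > 0.5) as the main measure, and say explicitly whether any detrending is applied.
3. In section E.4, prespecify a sensitivity analysis that replaces PPI with PPI minus the infant's chance PPI. Chance PPI is the same index computed from rSO2 and that infant's own MAP shifted in time, with the shift fixed in advance.
4. Treat linear detrending as at most a further sensitivity analysis. A 20-minute pressure fall followed by rSO2 is genuine passivity, and detrending can remove it. In an illustration where both signals share a random walk (step SD 1) plus independent noise, detrending cut detection from 98% to 91% with noise SD 1 and from 62% to 27% with noise SD 2. It also leaves 7% to 10% chance concordance at autocorrelation 0.9 or above, so it cannot replace the reference.

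The subtraction is approximate. If a share p of windows is truly passive and always detected, and the chance level is c, raw PPI is p + (1 − p)c and the difference is p(1 − c). That is zero when there is no passivity and slightly below p otherwise.

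The cost is a little more code for the central analyst and a second PPI figure to report. No new measurement is needed.

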##### Sample Size Estimate

This study would be done at eight centers with an estimated total enrollment of 100 infants over a one-year period. Literature is unavailable regarding expected differences in NIRS measures for preterm infants with CNS morbidity or mortality. One hundred infants will yield 80% power at the 0.05 level of significance to detect an association between NIRS measures and morbidity-free survival if 8% of the variance in low rSO2 index can be explained by the subsequent development of CNS-morbidity or mortality. Similar effect size can be expected for the predictor variable PPI. Power may be improved by the inclusion of covariates in the full logistic regression model.

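### Does the plan leave the pressure passivity index (PPI) undefined between one percentage per infant and a 0/1 value per 20-minute interval?

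*Combined protocol and SAP*

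**What the plan says.** Methods section 3 defines the index as "PPI (total percentage time with concordance between" cerebral saturation and mean arterial pressure. It says that mean saturation and PPI "will be calculated over 20 minute intervals. Concordance will be defined as a Pearson's correlation coefficient >0.5". Before that it says that missing time will be totalled, and it introduces the calculation with "Of the remaining useful NIRS data". It gives no minimum number of valid pairs for an interval. The sampling rate is 1/30 Hz.

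Study Design (Methods section 1) uses the same window: "Data will be analyzed in 20-minute intervals to determine the mean cerebral oxygenation", with PPI in the same list. It names both logistic regression and longitudinal modelling.

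Sample Size Estimate states that "One hundred infants will yield 80% power at the 0.05 level of significance" if outcome explains 8% of the variance in the low-saturation index. It adds "Similar effect size can be expected for the predictor variable PPI" and "Power may be improved by the inclusion of covariates in the full logistic regression model". Statistical Analysis then says: "Analyses will include mixed effects regression models for repeated measures to examine the relationship between NIRS measures", namely the low-saturation index and PPI, and the outcome.

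**The concern.** PPI is the exposure for Aim 2, so its unit matters. Concordance is a single threshold on a single correlation, and 20 minutes is the only window given. Taken interval by interval, PPI is therefore a 0/1 record, and a percentage appears only when intervals are pooled.

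Pooled over an infant's whole recording, PPI fits the power statement but leaves the repeated-measures model with nothing repeated. Kept by interval, it gives the model its repeats, but the 8% of variance seems not to carry over, because most of the variance of a 0/1 record lies within infants. No intermediate period, such as a day, is named. An analyst could in principle choose the level after seeing the data.

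The second worry is sparse intervals. A sample correlation from few pairs is noisy, so the chance of crossing 0.5 depends on how many pairs survive, and no minimum is set.

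**Working it through.** **Inputs from the documents.** 100 infants, 8% of variance, alpha 0.05, 80% power (Sample Size Estimate); 30-second sampling, 20-minute intervals, threshold 0.5 (Methods section 3); 96 hours of life, entry before 24 hours of age (Methods sections 1 and 2).

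**Assumptions.** Two-sided test; mean PPI 20% (Background reports this value for a different, coherence-based index, so it is only a working figure); between-infant SD of PPI 10 points, with 5 as a variant; 30% event rate where needed; intervals independent given the infant.

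**Counts.** 20 × 60 / 30 = 40 pairs per interval. 96 × 3 = 288 intervals per infant at most, or 72 × 3 = 216 if monitoring starts at 24 hours.

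**1. The plan's power figure, one value per infant.** Noncentrality = 100 × 0.08 / 0.92 = 8.70. The F test on 1 and 98 df gives power 83.1%. The Fisher z approximation, Φ(√97 × atanh(√0.08) − 1.96), gives 81.7%. Both are consistent with the stated 80%.

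**2. The same question with 0/1 interval records.** In a model with an infant random effect, outcome varies only between infants, so it is tested essentially against between-infant variation. The cost of binary records is the noise in each infant's mean.

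- Total variance of a 0/1 record: 0.20 × 0.80 = 0.16.
- Within-infant part: 0.16 − 0.10² = 0.15. Per infant mean: 0.15 / 288 = 0.00052.
- Reliability of the infant mean: 0.0100 / (0.0100 + 0.00052) = 0.950.
- Explained share after this dilution: 0.08 × 0.950 = 0.0760; noncentrality = 100 × 0.0760 / 0.9240 = 8.23.

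| Intervals | Between-infant SD | Reliability | Explained share | Power |
|---|---|---|---|---|
| 288 | 10 points | 0.950 | 7.6% | 81% |
| 216 | 10 points | 0.935 | 7.5% | 80% |
| 288 | 5 points | 0.821 | 6.6% | 75% |

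**3. Where a large discrepancy would come from.** If the 8% were applied to the raw variance of interval records, the PPI difference between infants with and without the outcome would have to be √(0.08 × 0.16) / √(0.3 × 0.7) = 0.113 / 0.458 = 24.7 points. At infant level it is √0.08 × 10 / 0.458 = 6.2 points. Sample Size Estimate speaks of 100 infants and of the infant's later outcome; nowhere does it claim 8% of interval-level variance. The 24.7 points therefore answer a question the plan does not ask.

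**4. Sparse intervals.** Simulated probability that the sample correlation exceeds 0.5:

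| True correlation | Sample dependence | 40 pairs | 30 | 20 | 10 |
|---|---|---|---|---|---|
| 0.3 | independent | 7.5% | 11.0% | 16.7% | 27.3% |
| 0.3 | lag-1 of 0.8 (assumed) | 24% | 27% | 31% | 36% |
| 0.7 | independent | 97.7% | 95.8% | 92.1% | 84.2% |
| 0.7 | lag-1 of 0.8 (assumed) | 86% | 84% | 81% | 78% |

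At a true correlation of 0.3, going from 40 to 10 pairs raises the probability 3.6-fold if samples are independent (27.3 / 7.5) and 1.5-fold with the assumed autocorrelation (36 / 24). Independence is unlikely for pressure and saturation read every 30 seconds.

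What enters an infant's PPI is the average over intervals. Suppose 10 to 20 gaps, each leaving two partial intervals with 3 to 39 pairs, and independent samples. Pooled PPI then moves from 7.5% to 8.3% (10 gaps) or 9.1% (20 gaps) at a true correlation of 0.3, and from 97.7% to 97.2% or 96.7% at 0.7.

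**The case for a change.** The strongest case for a change is textual. The definition and the interval wording share a sentence, Statistical Analysis names only the mixed model, and nothing assigns a form of PPI to a model. Study Design's pairing of logistic regression with longitudinal modelling permits a division (infant percentage in one, interval concordance in the other) but does not state it. The study has hypotheses and a powered comparison, so being a pilot does not excuse an open exposure definition. A sentence would settle it at almost no cost.

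What stands is that the level of PPI in the mixed model, and what makes an interval valid, are not written down; saying so would make the text clearer. Two stronger claims fail. The first is that no reading fits both the power statement and the model: Statistical Analysis says what analyses will include, which does not exclude the logistic regression named elsewhere, and the model also covers the low-saturation index, which is a true percentage in every interval. The second is that the power premise collapses at interval level; step 2 shows a loss of about 2 to 3 points at the assumed SD of 10, and about 8 points (83% to 75%) if the SD is only 5.

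The extreme sparse case is also fair to state: with independent samples and a true correlation of 0.3, if 10% to 30% of intervals had only 10 pairs, pooled PPI would be 9.5% to 13.5% (for example, 0.7 × 7.5 + 0.3 × 27.3 = 13.5). The documents do not say how common such intervals would be.

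**Conclusion.** This is a gap in wording that analysts would fill sensibly. A total percentage of time, with concordance judged interval by interval, reads naturally as the share of an infant's 20-minute intervals with a correlation above 0.5; the epoch-based index described in Background has the same form. That reading supports the logistic regression and the power statement, and the interval records remain available for the longitudinal model.

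No stated figure is wrong. Power is about 83% with one value per infant and 80% to 81% with 216 to 288 binary records, assuming a mean PPI of 20%, a between-infant SD of 10 points and intervals independent given the infant. It falls to 75% with 288 records if the SD is 5 points. A minimum pair count would be ordinary data cleaning; in the scenario of 10 to 20 gaps its absence shifts an infant's PPI by about 0.5 to 1.6 points. Replacing the repeated-measures model by one value per infant would give up the time course in the main analysis, which is a trade-off and not a correction. No change to the plan is needed.
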